4.5.3 Exploratory Immunogenicity Analysis Methods

Cell mediated immunity response variables described in [Section 3.4.1.2](#) will be summarized using descriptive statistics. The observed values and changes from

baseline will be presented for each visit where parameters are scheduled to be collected per the clinical study protocol.

Exploratory neutralizing antibody titer by pseudoviral microneutralization assay and binding antibody titer measured by MSD multiplex assay and ACE2 Panel 13 for variants described in [Section 3.4.1.2](#) will be summarized using similar methods to those described in [Section 4.5.2](#). For [name] Laboratory assays, geometric mean titers will be summarized in place of GMCs.

4.6 Safety Evaluation

Safety analysis will be carried out for the SS, to include all participants who receive at least one dose of study vaccine. Participants who do not complete the study, for whatever reason, will have all available data up until the time of termination included in the analysis. For safety analysis presented by study visit, the baseline value will be defined as the last value reported prior to first study vaccine administration.

4.6.1 *Extent of Exposure*

Extent of exposure to study vaccine will be summarized for the SS by study vaccine group for each cohort. The total number of participants receiving each dose and the total number of doses will be presented for both cohorts. The interval of time between vaccinations will be presented in days for Cohort A only, and calculated as the date of second vaccine administration minus the date of first vaccine administration, plus one. Total number of doses and interval of time between vaccinations will be summarized using descriptive statistics.

4.6.2 *Adverse Events*

Study AEs that occur post vaccination will be summarized by study vaccine group for each cohort. Events reported with a partial onset date (e.g., month and year are reported but the day is missing) will be considered to be post vaccination if it cannot be confirmed that the event onset was prior to vaccination based on the available date entries.

Verbatim terms on case report forms will be mapped to preferred terms and system organ classes using the Medical Dictionary for Regulatory Activities (MedDRA, version 24.0). Injection site tenderness will only be coded to the lower-level term, as there is no PT of injection site tenderness (coded to a PT of injection site pain).

Solicited and unsolicited AEs will be summarized separately. The number of participants reporting solicited AEs within 7 days of each vaccination will be summarized by cohort (or Sub-cohort for Cohort A), study vaccine group, vaccination (for Cohort A), and toxicity grade for each day, as well as over the entire 7-day period. The duration of solicited adverse events occurring within 7 days of each vaccination will be summarized with descriptive statistics and the number of participants reporting AEs ongoing after 7 days will also be presented. The number of participants reporting unsolicited AEs within 28 days of each vaccination and through the end of the study will be presented.

The number of participants reporting SAEs, MAAEs, AESIs, AEs leading to discontinuation/withdrawal of vaccination, or AEs leading to death will also be presented.

Summaries of unsolicited AEs that are displayed by system organ class and preferred terms will be ordered by descending incidence of system organ class and preferred term within each system organ class for the 154-01 study vaccine group. Summaries displayed by preferred term only will be ordered by descending incidence of preferred term for the 154-01 study vaccine group.

Summaries of the following types will be presented:

- Summary of solicited AEs within 7 days post each vaccination
- Summary of solicited AEs within 7 days post each vaccination by toxicity grade and day
- Summary of solicited AEs within 7 days post each vaccination by toxicity grade
- Summary of duration (days) of solicited AEs post each vaccination
- Overall summary of unique unsolicited AEs and participant incidence of AEs meeting various criteria, including (but not limited to), AESIs, AEs leading to discontinuation, SAEs, and deaths, within 28 days of each vaccine administration;
- Most frequently-occurring ($\geq 10\%$ Overall) unsolicited AEs within 28 days of each vaccination by preferred term
- Participant incidence of unsolicited AEs up to 28 days post each vaccination by MedDRA system organ class and preferred term;
- Participant incidence of unsolicited AEs up to 28 days post each vaccination by severity, MedDRA system organ class, and preferred term;
- Participant incidence of unsolicited AEs up to 28 days post each vaccination by relationship to study vaccine, MedDRA system organ class, and preferred term;
- Participant incidence of unsolicited AEs up to 28 days post each vaccination by relationship to study procedure, MedDRA system organ class, and preferred term;
- Overall summary of unique unsolicited AEs and participant incidence of AEs meeting various criteria, including (but not limited to), AESIs, MAAEs, AEs leading to discontinuation, SAEs, and deaths through end of study;
- Most frequently-occurring ($\geq 10\%$ Overall) unsolicited AEs through end of study by preferred term
- Participant incidence of unsolicited AEs post each vaccination through end of study by MedDRA system organ class and preferred term;

- Participant incidence of unsolicited AEs post each vaccination through end of study by severity, MedDRA system organ class and preferred term;
- Participant incidence of unsolicited AEs post each vaccination through end of study by relationship to study vaccine, MedDRA system organ class and preferred term;
- Participant incidence of unsolicited AEs post each vaccination through end of study by relationship to study procedure, MedDRA system organ class and preferred term;
- Overall summary of unique MAAEs post each vaccination and participant incidence of AEs meeting various criteria, including (but not limited to), AESIs, AEs leading to discontinuation, SAEs, and deaths;
- Participant incidence of MAAEs post each vaccination by system organ class, and preferred term;
- Participant incidence of related MAAEs post each vaccination by system organ class and preferred term;
- Participant incidence of SAEs post each vaccination by system organ class, and preferred term;
- Participant incidence of SAEs post each vaccination by relationship to study vaccination, system organ class, and preferred term;
- Participant incidence of SAEs post each vaccination by relationship to study procedure, system organ class, and preferred term;
- Participant incidence of AESIs post each vaccination by system organ class and preferred term; and
- Participant incidence of AEs leading to discontinuation/withdrawal post each vaccination by system organ class and preferred term; and
- Participant incidence of AEs leading to death post each vaccination by system organ class and preferred term.

At each level of summarization (e.g., any AE, system organ class, and preferred term), participants experiencing more than one AE will be counted only once. In the summary of AEs by toxicity or severity grade, participants will be counted once at the highest toxicity or severity reported at each level of summarization; in the summary of unsolicited AEs by relationship, participants will be counted once at the closest relationship to study vaccine or procedure. Related events include those relationship to study vaccine or procedure is reported as “Possible,” “Probable,” or “Definite;” events considered not related are those reported as “Unrelated” to study vaccine or procedure. The total number of patients reporting events in each individual relationship category will also be summarized, in addition to the “Related” and “Unrelated” categories.

Adverse event data will be presented in data listings by sub-cohort (Cohort A only), participant, study vaccine group, and event.

Graphical representations of frequencies of solicited and unsolicited AEs may also be provided.

4.6.3 Deaths, Other Serious Adverse Events, and Other Significant Adverse Events

All deaths during the study, including the post study vaccine follow-up period, will be listed by participant, to include the primary cause of death. Serious AEs, MAAEs, and other significant AEs, including those that led to discontinuation of study vaccine or withdrawal from study will be provided in separate participant data listings.

4.6.4 Clinical Laboratory Evaluation

All descriptive summaries of laboratory results will be based on data analyzed by the local laboratories and presented in Système International (SI) units, as suggested by the Center for Biologics Evaluation and Research and the Center for Drug Evaluation and Research *Position on Use of SI Units for Lab Tests* (Oct 2013). All data will be included in by-participant data listings. Laboratory measurements identified as abnormal (i.e., outside the normal range) will also be listed separately by participant, laboratory test, and unit. In addition, normal ranges provided by the local laboratories will be presented in a separate listing.

Clinical laboratory measurements, including serum chemistry and hematology, will be summarized study vaccine group for each cohort. Descriptive statistics will be presented for observed values and changes from baseline at each visit where parameters were scheduled to be collected per the clinical study protocol.

Where applicable, laboratory results will be classified as “low,” “normal,” or “high” with respect to the parameter-specific reference ranges (i.e., below the lower limit of the normal range, within the normal range, or above the upper limit of the normal range). Three-by-three contingency tables will be presented for each laboratory parameter to summarize the shift from the baseline category to the worst post-baseline measurement, defined as the value numerically farthest outside of the normal range across all post-baseline visits through the end of the study.

Summary results will include the count and percentage of participants within each shift category and study vaccine group.

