6.2 Study Assessments and Visits

6.2.1 Cohort A Visits

The Schedule of Assessments for Cohort A (including Sub-cohorts A1 and A2) is located in [Appendix 1](#).

Participants in Cohort A are followed for 12 months post-second dose of the study vaccine until Day 394. Study vaccines are administered on Days 1 and 29 where safety and immunogenicity assessments are also performed prior to administration of the study vaccine. Clinic visits including safety laboratories should occur 3, 7, and 28 days post-vaccination (Days 4, 8, 29, 32, 36, and 57). Clinic visits including blood collection to measure the participant's immune response to the study vaccine should occur on Days 15, 29, 43, 57, 119, 209, 299, and 394 (Final Visit).

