7.5.3 Safety Analysis

Safety, reactogenicity, and safety laboratory assessments will be evaluated in the Safety set. Participants will be summarized according to the study vaccine that was received.

Descriptive statistics will be provided for each solicited AE and for each study vaccine group. Local and systemic AEs from Day 1 through Day 7 after each vaccination will be presented by severity cumulatively using a 5-point toxicity grading scale (Grades 0 through 4). Descriptive summary statistics will include counts and percentages of participants with the indicated endpoint.

Descriptive statistics will also be provided for abnormal hematology and chemistry laboratory values at Day 1 and at 3, 7 and 28 days following each dose of the study vaccine, including shifts in toxicity grading (DHHS 2007). Descriptive summary statistics will include counts and percentages of participants with the indicated endpoint.

Unsolicited AEs (including MAAEs, SAEs, and AEs leading to discontinuation/withdrawal) will be categorized according to MedDRA terms. Descriptive summary statistics (counts, percentages) will be provided for any unsolicited AE event in each study vaccine group.

Missing solicited AE diary data will not be imputed; missing AE dates will be handled according to the rules defined in the SAP.

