In general, non-zero percentages will be rounded to one decimal place, with the exception of “100%” which will be displayed without any decimal places. Select immunogenicity parameters will be rounded to additional decimal places, if warranted by the nature of data collection. When categorical data are presented, the percentages will be suppressed when the frequency count is equal to zero. Rounding conventions for presentation of summary statistics will be based on the precision of the variable of summarization, as it is collected in its rawest form (i.e., on the electronic case report form [eCRF] or as provided within an external file) and are outlined as follows:

- The mean and median will be rounded to one more decimal place than the precision of the variable of summarization;
- Measures of variability (e.g., SD, SE) will be rounded to two more decimal places than the precision of the variable of summarization; and
- Minimum and maximum values will be presented using the same precision as the variable of summarization.

Other statistics (e.g., CIs) will be presented using the same general rules outlined above, or assessed for the most appropriate presentation based on the underlying data.

No formal statistical analysis will be performed to compare study vaccine groups. This study is exploratory in nature; descriptive statistics will be tabulated by cohort and study vaccine group and reviewed to evaluate all study endpoints.

4.1.2 *Summarization by Visit*

Data summarized by study visit will be based on the nominal, scheduled visit label as reported on the eCRF. Data collected for the last participant visit completed will be summarized separately for:

- The scheduled Final Visit (defined as 365 days after the last study vaccine dose) for those participants who complete the scheduled end of study visit, per protocol; and
- The last visit completed on-study, combining data collected for participants who complete the Final Visit as well as the early termination visit for those participants who discontinue the study early. This summary will be labelled as “Final Visit / Early Termination” in the analysis.

Data collected at unscheduled visits will not be included in by-visit summaries, but will be considered when endpoint derivations potentially include multiple visits (e.g., determination of baseline value, determination of worst post-baseline value, etc.). All data will be included in participant listings.

4.1.3 *Data Handling Rules*

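### The laboratory shift table counts each participant in one direction only, so a participant who is both low and high on the same parameter loses one abnormality from that table

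*SAP*

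**What the plan says.** SAP 4.6.4 classifies results as low, normal or high "with respect to the parameter-specific reference ranges". It then states: "Three-by-three contingency tables will be presented for each laboratory parameter to summarize the shift from the baseline category to the worst post-baseline measurement". The worst measurement is "defined as the value numerically farthest outside of the normal range across all post-baseline visits through the end of the study". The section plans no separate shift to the lowest or the highest value, and no category for participants who were both low and high.

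Under SAP 4.1.2, unscheduled results are kept out of the by-visit summaries but do feed the derivation of a worst post-baseline value. SAP 4.6 sets the safety baseline as the last value before the first vaccination. In Cohort A the post-baseline period therefore spans both doses.

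The same section plans other laboratory outputs. All data are listed, and: "Laboratory measurements identified as abnormal (i.e., outside the normal range) will also be listed separately by participant, laboratory test, and unit". It also says: "Descriptive statistics will be presented for observed values and changes from baseline at each visit where parameters were scheduled to be collected". Under SAP 4.1.1 those statistics include the minimum and maximum.

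**The concern.** The rule compares distances below the range with distances above it, in raw units, and keeps only the larger. A low and a high on the same parameter are different findings, and a participant can have both. The table records one and drops the other, and the choice turns on units and range limits rather than on clinical weight.

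The comparison is not symmetric. A non-negative analyte cannot lie farther below its range than the lower limit itself, whereas nothing caps the distance above. Where the lower limit is small, a modest high can outrank a marked low.

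This matters because the shift table is the only laboratory table in SAP 4.6.4 that counts participants by type of abnormality. Listings do not give incidence by arm, and a group minimum does not say how many participants were low. Safety is a primary objective and is assessed descriptively, so the counts themselves are the result.

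**Working it through.** The plan gives no figure on this point, so there is none to reproduce. It also gives no numeric reference ranges or abnormality rates. All ranges and rates below are assumptions.

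**Inputs from the documents**
- Scheduled post-baseline safety draws in Cohort A: Days 4, 8, 29, 32, 36 and 57, so k = 6 (Protocol 6.2.1).
- Scheduled post-baseline safety draws in Cohort B: Days 4, 8 and 29, so k = 3 (Protocol 6.2.2).
- Planned arms (Protocol 3.1): A1 is 12 at 1:1:1, giving 4 each. A2 is 24 at 3:1, giving 18 and 6. B is 36 at 1:1:1, giving 12 each.

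**Step 1: apply the rule as written.** Let LLN and ULN be the lower and upper limits of normal. Distance is LLN − x if x < LLN, x − ULN if x > ULN, and 0 otherwise. The value with the largest distance is kept. Each row is one participant with both values on one parameter.

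| Parameter (assumed range) | Low value, distance | High value, distance | Shown as |
|---|---|---|---|
| Neutrophils (2.0–7.5) | 0.9, 1.1 | 8.8, 1.3 | high only |
| WBC (4–11) | 2.4, 1.6 | 13, 2.0 | high only |
| Platelets (150–400) | 95, 55 | 470, 70 | high only |
| Potassium (3.5–5.1) | 2.9, 0.6 | 5.5, 0.4 | low only |

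In the neutrophil row the discarded value is 1.1/2.0 = 55% below its limit, and the retained one is 1.3/7.5 = 17% above its limit. The potassium row shows the loss in the other direction.

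**Step 2: the cap.** The largest possible distance below the range is LLN, so any value above ULN + LLN displaces every possible low. For the assumed neutrophil range that is 7.5 + 2.0 = 9.5. For platelets it is 400 + 150 = 550.

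**Step 3: how often both directions occur.** Let q be the chance per visit of falling in each tail, with visits independent. The chance of at least one low and at least one high in k visits is

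P = 1 − 2(1 − q)^k + (1 − 2q)^k.

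For q = 5% and k = 6: 1 − 2(0.7351) + 0.5314 = 0.0613.

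| q per tail per visit | Cohort A, k = 6 | Expected of 36 | Cohort B, k = 3 | Expected of 36 |
|---|---|---|---|---|
| 1% | 0.3% | 0.1 | 0.06% | 0.02 |
| 2.5% | 1.7% | 0.6 | 0.4% | 0.1 |
| 5% | 6.1% | 2.2 | 1.4% | 0.5 |

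These are per parameter. Under the assumptions they are upper limits for omitted lows, because a low is dropped only when the high lies farther out. Unscheduled results are not included.

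**Step 4: weight of one omission.** 1/18 = 5.6, 1/12 = 8.3, 1/6 = 16.7 and 1/4 = 25 percentage points.

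**Step 5: after the change.** With separate lowest-value and highest-value shifts, each participant in Step 1 has one low entry and one high entry. Nothing is displaced.

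**The case against.** The best defence is that nothing is lost from the report. Every result is listed, abnormal results are listed again, and a scheduled result enters the by-visit statistics. A clinically significant abnormality may also be recorded as an adverse event (Protocol 6.3.1.2.16). With arms of 4 to 18, the listings can be read participant by participant. The trial is descriptive, and no test or decision rule uses this table. All of this stands, and it limits the point to the shift table. It does not supply the missing count: an unscheduled low displaced by a high would appear in the laboratory listings but in no laboratory summary table.

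It is also fair to say that the event is uncommon and the neutrophil example is close. With the same 0.9, a later value of 8.5 (1.0 above) instead of 8.8 would leave the participant shown as low. If participants tend to stay on one side of the range, both directions occur less often than Step 3 suggests.

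A reader might infer three stronger claims, which the documents do not support:
- **That the rule favours high for blood counts in general.** The tilt depends on the analyte's range and its usual excursions. Where the lower limit is large relative to plausible falls, the cap has no practical effect.
- **That the sampling schedule was built to detect low counts.** No section says so, and Table 1 of the protocol does not list low counts among the risks.
- **That pooling visits removes timing altogether.** By-visit statistics keep the timing of values. Protocol 7.5.3 does promise abnormal-value summaries "at Day 1 and at 3, 7 and 28 days following each dose of the study vaccine, including shifts in toxicity grading", and SAP 4.6.4 describes no toxicity-grade shift. That is a separate gap, and two-direction shifts do not close it.

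**Conclusion.** The point holds for the shift table and no further. As written, the rule omits one direction for any participant with both a low and a high on the same parameter. The omitted direction is more easily the low where the lower limit is small, and it can be the high elsewhere.

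The expected frequency is low: about 0.3% to 6.1% of Cohort A and 0.06% to 1.4% of Cohort B participants per parameter. Those figures rest on assumed tail rates of 1% to 5% per visit and on independent visits, and the worked examples rest on assumed ranges. The 5.6 to 25 points describe one omission once it has happened, not an expected bias. Sample size and error rates are unaffected. Severity is minor.

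**What to change.** In SAP 4.6.4, replace the single worst-value shift with two for each parameter: baseline category to the lowest post-baseline value, and baseline category to the highest. State that a participant may count as low in one and high in the other, and that unscheduled results feed both.

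The cost is one additional shift table per parameter, with no new data. Presenting the shifts by dose period is optional. In Cohort A it would give 2 directions × 2 doses = 4 tables per parameter in place of one; Cohort B would stay at two. A dose-period split would still pool the 3-, 7- and 28-day draws, so it should not be offered as the answer to Protocol 7.5.3. This is a cheap improvement.

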4.6.5 Vital Signs, Physical Findings, and Other Observations Related to Safety

4.6.5.1 Vital Signs and Pulse Oximetry

Vital sign and body temperature parameter measurements will be summarized by study vaccine group for each cohort. Descriptive statistics will be presented for results and change from baseline at each visit where parameters were scheduled to be collected. Results will also be presented in participant data listings.

Pulse oximetry results collected as part of the solicitation of information relating to COVID-19 cases will be presented in participant data listings.

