1.7 Risk Benefit Assessment

1.7.1 Potential Risks

The potential benefits and risks of ARCT-165/ARCT-154 are informed by the non-clinical and clinical studies conducted with ARCT-021 and non-clinical pharmacology studies conducted with ARCT-165 and ARCT-154. Detailed information about the potential benefits and risks and reasonably expected AEs of ARCT-021, ARCT-154, and ARCT-165 is provided in the IB ([Arcturus 2022a](#)). A summary of the potential risks of treatment with ARCT-021, ARCT-154, and ARCT-165, together with potential mitigation for these risks, is shown in [Table 1](#). As of protocol Version 3.0, the ongoing review of safety data from the ARCT-154-01 and ARCT-021-04 had not identified any confirmed new risks with use of the ARCT-154 and ARCT-165 vaccines. However, hypertension is being evaluated as a signal based on blinded safety data from the ARCT-154-01 study.

Table 1 Risk Minimization Measures Included in Clinical Studies of ARCT-021, ARCT-154, and ARCT-165

Risk	Mitigation

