6.1.2 Vital Signs and Body Temperature

VS comprise heart rate (HR), blood pressure and respiratory rate.

VS will be measured in a semi-supine position after 5 minutes of rest. VS and body temperature will be evaluated for clinical significance. Any clinically significant change in VS and body temperature should be evaluated for underlying cause and the associated AE reported. If no known cause is determined, the clinically significantly abnormal parameter may be reported as an AE.

After each study vaccine administration, vital signs should be checked, and repeat vital signs should be taken if clinically indicated.

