6.3.1.2.16 Laboratory Test Abnormalities

Clinically significant abnormal laboratory test results, in the opinion of the Investigator, may constitute or be associated with an AE. Examples of these include abnormal laboratory results that are associated with symptoms or require treatment, e.g., bleeding due to thrombocytopenia, tetany due to hypocalcemia, or cardiac arrhythmias due to hyperkalemia. Whenever possible, the underlying diagnosis should be listed in preference to abnormal laboratory values as AEs. Severity grading of abnormal test results should follow the grading of unsolicited AEs when the event is deemed clinically significant by the Investigator (Section [6.3.1.2.9](#)). Clinically significant abnormalities will be monitored by the Investigator until the parameter returns to its baseline value or until agreement is reached between the Investigator and Sponsor Medical Monitor (or designee) that further follow-up is not required. Laboratory abnormalities deemed NCS by the Investigator should not be reported as AEs. Similarly, laboratory abnormalities reported as AEs by the Investigator should not be deemed NCS on the laboratory sheet. Where relevant, safety laboratory assessments will be analyzed by toxicity grade at the time of interim and final analysis.

The Investigator is responsible for reviewing and signing all laboratory reports. The signed clinical laboratory reports will serve as source documents and should include the Investigator's assessment of clinical significance of out of range/abnormal laboratory values.

A list of laboratory analytes to be tested is included in [Appendix 3](#).

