6.5 Vital Signs and Body Temperature

VS and body temperature will be evaluated for clinical significance. Any clinically significant change in VS or body temperature should be evaluated for an underlying cause and the associated AE reported. If no known cause is determined, the clinically significantly abnormal parameter may be reported as an AE. Severity grading of clinically significant abnormal VS should follow the grading of unsolicited AEs when the event is deemed clinically significant by the Investigator (Section [6.3.1.2.9](#)). All collected VS will also be analyzed by toxicity grade at the time of interim and final analyses.

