APPENDIX 5 TOXICITY GRADING SCALE SOLICITED ADVERSE EVENTS

Solicited Local AEs	Grade 0	Grade 1 (Mild)	Grade 2 (Moderate)	Grade 3 (Severe)	Grade 4 (Potentially Life Threatening)
Injection Site Erythema *	<2.5 cm	2.5–5 cm	5.1–10 cm	>10 cm	Emergency Room (ER) visit, hospitalization or necrosis or exfoliative dermatitis
Injection Site Induration/Swelling **	<2.5 cm	2.5–5 cm and does not interfere with activity	5.1–10 cm or interferes with activity	>10 cm or prevents daily activity	ER visit or hospitalization or necrosis
Injection Site Pain	None	No interference with activity	Some interference with daily activity or leads to use of non-narcotic pain reliever for >24 hours	Prevents daily activity or leads to use of narcotic pain reliever	ER visit or hospitalization
Injection Site Tenderness	None	Mild discomfort to touch	Discomfort with movement	Significant discomfort at rest	ER visit or hospitalization
Solicited Systemic AEs					
Fever (°C)*** (°F) ***	<38.0 <100.4	38.0–38.4 100.4–101.1	38.5–38.9 101.2–102.0	39.0–40 102.1–104	>40 >104
Nausea/vomiting	None	No interference with activity or 1–2 episodes/24 hours	Some interference with activity or >2 episodes/24 hours without seeking medical attention	Prevents daily activity or requires outpatient IV hydration	ER visit or hospitalization for hypotensive shock
Diarrhea	<2 loose stools/24 hours	2–3 loose stools or <400 g/24 hours	4–5 stools or 400–800 g/24 hours	6 or more loose or watery stools or >800 g/24 hours or requires outpatient IV hydration	ER visit or hospitalization
Headache	None	No interference with activity	Some interference with daily activity or leads to use of non-narcotic pain reliever >24 hours	Significant; prevents daily activity or leads to use of narcotic pain reliever	ER visit or hospitalization

Solicited Local AEs	Grade 0	Grade 1 (Mild)	Grade 2 (Moderate)	Grade 3 (Severe)	Grade 4 (Potentially Life Threatening)
Fatigue	None	No interference with activity	Some interference with activity	Significant; prevents daily activity	ER visit or hospitalization
Myalgia	None	No interference with activity	Some interference with activity	Significant; prevents daily activity	ER visit or hospitalization
Arthralgia, chills, dizziness	None	No interference with activity	Some interference with activity but does not require medical intervention	Prevents daily activity and requires medical intervention	ER visit or hospitalization

Abbreviation: ER=emergency room

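### The SAP omits the protocol's toxicity-grade analyses of vital signs and laboratory values, while its Section 4.10 declares no change

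*SAP*

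**What the plan says.** **Vital signs.** Protocol Section 6.1.2 defines the set: "VS comprise heart rate (HR), blood pressure and respiratory rate". Section 6.5 first deals with changes that become adverse events: "Severity grading of clinically significant abnormal VS should follow the grading of unsolicited AEs". It then adds a second commitment: "All collected VS will also be analyzed by toxicity grade at the time of interim and final analyses". SAP Section 4.6.5.1 plans this: "Descriptive statistics will be presented for results and change from baseline at each visit where parameters were scheduled to be collected". It adds participant listings and mentions no grade.

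**Laboratory values.** Protocol Section 6.3.1.2.16 says: "Where relevant, safety laboratory assessments will be analyzed by toxicity grade at the time of interim and final analysis". Section 7.5.3, in the statistical part of the protocol, is more specific. Abnormal hematology and chemistry values are to be summarised "at Day 1 and at 3, 7 and 28 days following each dose of the study vaccine, including shifts in toxicity grading (DHHS 2007"). SAP Section 4.6.4 plans observed values and changes by visit, a listing of abnormal values, and a three-by-three low/normal/high table from baseline to the single worst post-baseline value.

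**Changes from the protocol.** SAP Section 1 undertakes to explain any change from the protocol's statistical methods. SAP Section 4.10 reports no changes to the planned analyses. Its one clarification is that the ancestral strain was not available for the microneutralization assay.

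**The concern.** Anyone programming from the SAP would drop one safety summary that the protocol specifies and produce a coarser version of another, and nothing in the SAP would warn them. In a study with no hypothesis tests, the pre-specified descriptive tables are the safety result, so an undeclared omission matters more than it would as a side table in a confirmatory trial.

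What would be lost is a count, by vaccine group, of how many participants reached each grade. A low/normal/high category holds a small excursion and a large one together. For vital signs the omission touches a parameter that the protocol itself is watching: "hypertension is being evaluated as a signal based on blinded safety data from the ARCT-154-01 study".

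**Working it through.** No formula or stated figure is involved. The check compares the texts and counts what was carried over.

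**Step 1: is the vital-sign promise separate from AE grading?** Yes. Section 6.5 gives AE severity grading only to changes judged clinically significant. The next commitment covers all collected vital signs and is introduced as additional, so AE tables by severity do not fulfil it.

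**Step 2: the two plans side by side.**

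| Item | Protocol | SAP |
|---|---|---|
| Vital signs by toxicity grade | Promised (6.5) | Absent (4.6.5.1) |
| Laboratory shift categories | DHHS 2007 toxicity grade (7.5.3) | Low/normal/high against the local range (4.6.4) |
| Laboratory shift timing | 3, 7 and 28 days after each dose (7.5.3) | One worst value across all post-baseline visits (4.6.4) |
| Disclosure of a change | To be explained with reasons in the SAP or CSR (Section 7) | None declared (4.10) |

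Graded analyses carried over: 0 of 2.

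**Step 3: does the SAP use toxicity grade elsewhere in a way that covers this?** SAP Section 4.6.2 lists 25 types of AE summary. Two use toxicity grade (by grade and day, and by grade), and both concern solicited AEs. SAP Section 3.4.2.1 likewise ties the 5-point scales to solicited AEs. Fever is graded there as a diary event, but heart rate, blood pressure and respiratory rate are not.

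**Step 4: is a vital-sign scale available?** Section 6.5 names none. Protocol Appendix 5 is titled "TOXICITY GRADING SCALE SOLICITED ADVERSE EVENTS" and has a row for 0 of the 3 parameters in Section 6.1.2. The scale still has to be named.

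**Step 5: what the laboratory substitution hides.** Protocol Appendix 3 gives post-dose laboratory days 4, 8, 29, 32, 36 and 57 in Cohort A (6 days: 3 after each dose) and 4, 8 and 29 in Cohort B (3 days). One worst value per participant therefore merges both doses in Cohort A. Exclusion criterion 20 removes liver tests only above 1.5 times the upper limit of normal, so a participant can enter already high. Any further rise, however large, then stays in the high-to-high cell. SAP Section 4.1.2 lets unscheduled laboratory values enter the worst-value derivation, but they still carry no grade.

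**Step 6: what the vital-sign plan leaves out.** SAP Section 4.1.2 keeps unscheduled readings out of by-visit summaries and admits them only to derivations across visits. Section 4.6.5.1 has no such derivation, so an unscheduled blood pressure appears only in a listing, unless it is reported as an AE.

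**Step 7: Section 4.10.** Its clarification concerns an assay strain and bears on neither analysis. The statement of no change is therefore incorrect on both.

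**The case against.** The strongest case is that little is really lost. SAP Section 4.1.1 reports minimum, maximum and quartiles for continuous variables, so the largest scheduled blood pressure or laboratory value per group and visit will be visible in the tables. Planned groups are small: 12/3 = 4 each in Sub-cohort A1, 18 and 6 in Sub-cohort A2 (24 split 3:1), and 36/3 = 12 each in Cohort B. Graded counts in such groups add limited information. Blood pressure is also followed by repeated measurement, AE tables by severity and an individual stopping rule. The hypertension signal comes from blinded data in another study.

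The two halves also differ in strength. The laboratory commitment sits in the statistical section and names its scale. The vital-sign commitment is one sentence in an assessment section, is not repeated in Protocol Section 7, and cannot be carried out without a scale that the protocol does not supply. That gap begins in the protocol. Finally, the SAP may be amended for Cohort A before database lock, and its silence need not be a decision to drop anything.

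Most of this stands as to weight. It does not remove the inconsistency. A maximum shows one participant's extreme, not how many participants reached a grade, and it omits unscheduled readings. The qualifier about relevance applies to Section 6.3.1.2.16 and not to the grade shifts in Section 7.5.3. A missing scale is a reason for the SAP to name one or to declare the omission. The possibility of amendment does not correct the present text.

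**Conclusion.** The concern holds. Both graded safety analyses that the protocol promises for vital signs and laboratory values are missing from the SAP, and Section 4.10 is wrong to report no change. The laboratory half is the firmer of the two.

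The consequence is moderate. The tables would cover all planned participants (12 + 24 + 36 = 72), but no participant's data, treatment or follow-up is affected. The analyses support the safety objective and are not components of Endpoint 1. Individual values remain in listings, and clinically significant changes can still reach the AE tables. The loss is the graded summary by vaccine group and, for Cohort A laboratory shifts, the separation by dose.

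This rests on the SAP text. Table templates that the SAP mentions were not available; if they contain graded tables, the SAP text and Section 4.10 still need to agree with them.

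**What to change.** - **SAP 4.6.4:** add laboratory shifts in DHHS 2007 toxicity grade at 3, 7 and 28 days after each dose, by vaccine group, and by sub-cohort for Cohort A. The low/normal/high table can stay beside them.
- **SAP 4.6.5.1:** add counts and percentages of participants by vital-sign toxicity grade, with the same grouping, and name the grading scale. Choose the scale before unblinded values are seen.
- **Alternative:** if either analysis is not wanted, state and justify its omission in SAP 4.10.
- **SAP 4.10:** correct the statement of no change if either analysis is left out or altered, and in any case make it consistent with the revised Sections 4.6.4 and 4.6.5.1.

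As an optional layout that goes beyond the protocol's commitment, the maximum post-dose grade per participant and dose, including unscheduled readings, would present the vital signs compactly.

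The cost is a few descriptive tables from data already collected, plus the text changes. No protocol amendment is needed to add these tables, because the protocol already promises them.
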